### **5. TREATMENT PLAN**

#### **5.1 Treatment Regimen**

The investigational therapy used in the course of this study is BKM120. Treatment with BKM120 starts 2 weeks prior to cisplatin and radiotherapy and continues until the end of radiotherapy.

Study medication will be self-administered by the patients continuously throughout radiation. In order to assure compliance with protocol procedures drug administration will be thoroughly explained to the patients. During the study, BKM120 will be administered orally. It is given every day including weekend days. Administration of BKM120 stops with the end of radiotherapy. If radiation is held due to toxicity, BKM120 and cisplatin will be held as well. If cisplatin is held due to toxicity, BKM120 and radiation will continue. If BKM120 is held due to toxicity, cisplatin and radiation will continue. Medication labels will comply with US legal requirements and be printed in English. The storage conditions for study drug will be described on the medication label.

BKM120 will be provided by Novartis Pharmaceuticals free of charge. BKM120 is formulated as capsules for oral administration of 10mg and 50mg strength. Capsules are packaged in bottles. BKM120 capsule cannot be crushed and has to be swallowed. It cannot be given via enteral feeding tube.

If vomiting occurs, no attempt should be made to replace the vomited dose.

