**Table 9: Criteria for Defining Dose-Limiting Toxicities**

TOXICITY	ANY OF THE FOLLOWING CRITERIA
Hematologic a	≥ CTCAE grade 3 neutropenia for > 7 consecutive days
	CTCAE grade 3 thrombocytopenia for > 7 consecutive days
	CTCAE grade 4 thrombocytopenia
	Febrile neutropenia (ANC < 1.0 x 10  /L, fever ≥ 38.5°C)
Renal	Serum creatinine ≥ 2.0 x ULN to ≤ 3.0 x ULN for > 7 consecutive days
	> CTCAE grade 3 serum creatinine
Hepatic b	Total bilirubin ≥ 2xULN to ≤ 3.0 x ULN for > 7 consecutive days
	> CTCAE grade 3 total bilirubin
	CTCAE grade 3 AST or ALT for > 7 consecutive days
	CTCAE grade 4 AST or ALT
Endocrine	Grade 2 hyperglycemia (confirmed with a repeat FPG within 24 hours) that does not resolve to grade 0 within 14 consecutive days (after initiation of glimepiride, metformin or glibenclamide)
	≥ Grade 3 hyperglycemia (confirmed with a repeat FPG within 24 hours)
Metabolic/Laboratory	CTCAE grade 3 asymptomatic amylase and/or lipase, not reversible to ≤ CTCAE grade 2 for > 7 consecutive days
	CTCAE grade 4 asymptomatic amylase and/or lipase
Pancreatitis	≥ CTCAE grade 2
Cardiac	Cardiac toxicity ≥ CTCAE grade 3 or cardiac event that is symptomatic or requires medical intervention
	Clinical signs of cardiac disease, such as unstable angina or myocardial infarction, or Troponin ≥ CTCAE grade 3
Neurotoxicity	≥ 1 CTCAE grade level increase
Mood alteration	CTCAE grade 2 mood alteration that does not resolve to ≤ grade 1 within 14 days despite medical treatment (for Anxiety only, if worsened from baseline)
	≥ CTCAE grade 3 mood alteration
Dermatologic	Any phototoxicity ≥ CTCAE grade 2, or skin toxicity (rash) resulting in interruption of BKM120 for > 21 consecutive days
Other adverse events	≥ CTCAE grade 3 adverse events (excluding ≥ CTCAE grade 3 elevations in

	alkaline phosphatase)
	≥ CTCAE grade 3 vomiting or CTCAE grade 3 nausea despite the use of standard anti-emetics
	≥ CTCAE grade 3 diarrhea despite the use of optimal anti-diarrhea treatments
	CTCAE grade 3 fatigue (asthenia) for > 7 consecutive days CTCAE grade 4 fatigue (asthenia)

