
a ≥ CTCAE grade 3 anemia will not be considered DLT unless judged to be a hemolytic process secondary to study drug. ≥ CTCAE grade 3 lymphopenia will not be considered DLT unless clinically significant.
 
b For any grade 3 or 4 hepatic toxicity that does not resolve within 7 days to ≤ grade 1 (or ≤ grade 2 if liver infiltration with tumor present), an abdominal CT scan has to be performed to assess if it is related to disease progression.
 
A single patient is assumed not to tolerate the dose if he/she experiences at least one DLT. If a lower grade AE leads to a dose interruption of more than 7 doses of BKM120, this AE will be considered as DLT.
 
If the 2nd occurrence of an initially non-dose limiting toxicity (e.g., grade 3 AST that resolved to ≤ grade 1 within 7 days at 1st occurrence) leads to a dose reduction ( Section 6) within 28 days of the first dose of BKM120, this will be considered a DLT.
	

The investigator must notify the sponsor immediately of any unexpected ≥ CTCAE grade 3 adverse events or laboratory abnormalities. Prior to enrolling patients into a higher dose level, ≥ CTCAE grade 2 adverse events will be reviewed for all patients at the current dose level.

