## 5.6 Follow-up for dose-limiting toxicities

Patients whose treatment is interrupted or permanently discontinued due to an adverse event or clinically significant laboratory value, must be followed as outlined in Table 10, at least once a week for 4 weeks, and subsequently at 4-week intervals, until resolution or stabilization of the event, whichever comes first. If a patient requires a dose delay of > 14 days from the intended day of the next scheduled dose, then the patient should be discontinued from the treatment but will only come off study if dead or due to refusal to continue on the study. All patients must be followed for adverse events and serious adverse events for 28 days following the last dose of BKM120.

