## **5.7 Monitoring of BKM120 suspected toxicities**

Patients whose treatment is interrupted or permanently discontinued due to an adverse event or clinically significant laboratory value, must be followed as outlined in Table 10, at least once a week for 4 weeks, and subsequently at 4-week intervals, until resolution or stabilization of the event, whichever comes first. If a patient requires a dose delay of > 14 days from the intended day of the next scheduled dose, then the patient should be discontinued from study treatment. If the patient requires more than 2 dose reductions, the patient should be discontinued from study treatment. All patients must be followed for adverse events and serious adverse events for 28 days following the last dose of BKM120. All SAEs must be reported to Novartis as detailed in section 5.12.11 and 5.12.12.

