Grade 4 (> 500 mg/dL) [<math>\geq</math> 27.8 mmol/L]	
 
• immediately omit BKM120, initiate or intensify medication with appropriate anti-diabetic treatment, re-check within 24 hours. if grade improves then follow specific grade recommendations. If FPG is confirmed at Grade 4:               
 
• administer intravenous hydration and intervention for electrolyte/ketoacidosis/hyperosmolar disturbances as clinically appropriate
 
• discontinue patient from BKM120
 
• instruct patient to follow dietary guidelines according to local and/or institutional standards for management of diabetes mellitus (such as those provided by the American Diabetes Association) during the study
 
• consider use of oral anti-hyperglycemic therapy such as metformin
 
• check FPG at least weekly for 8 weeks, then continue checking at least every 2 weeks if clinically indicated
 
 
 
 
For non-fasting plasma glucose >500 mg/dL (> 27.8 mmol/L) accompanied by signs/symptoms of hyperglycemia (for example, mental status changes, excessive thirst, polyuria), or presence of blood or urine ketones, discontinue BKM120 and following guidance for management of Grade 4 fasting plasma glucose (FPG).

Recommended Dose Modifications for BKM120	
Worst toxicity (CTCAE Grade)**	Recommended Dose Modifications
CARDIAC	
Cardiac – Left Ventricular systolic dysfunction	
Asymptomatic, resting ejection fraction 50 – 40%; or 10-20% drop from baseline	Maintain dose level
Symptomatic, responsive to intervention, ejection fraction 39 – 20% or > 20% drop from baseline	Omit dose until resolved to ≤ Grade 1, then ↓ 1 dose level LVEF measurement to be repeated, if not resolved to ≤ Grade 1 within 3 weeks, permanently discontinue patient from BKM120
Refractory or poorly controlled, ejection fraction < 20%	Omit dose and discontinue patient from BKM120
Cardiac – QTc prolongation	

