Grade 3	
Omit dose until resolved to <math>\leq</math> Grade 1, then <math>\downarrow</math> 1 dose level (co-medicate)
 
Note: If question 9 on the PHQ-9 has a positive response, or worsens in severity, the patient should be referred for psychiatric consult regardless of the total questionnaire score

Grade 4	
Omit dose and discontinue patient from study
 
Note: If question 9 on the PHQ-9 has a positive response, or worsens in severity, the patient should be referred for psychiatric consult regardless of the total questionnaire score

Rash	
Grade 1	Maintain dose level. Consider to initiate appropriate skin toxicity therapy (such as antihistamines, topical corticosteroids)
Grade 2	Maintain dose level. Initiate/intensify appropriate skin toxicity therapy (such as antihistamines, topical corticosteroids)
Grade 3	
Omit dose until resolved to CTCAE Grade <math>\leq</math> 1, then:
 
 
If resolved in <math>\leq</math> 7 days, <math>\downarrow</math> 1 dose level
 
If resolved in <math>></math> 7 days (despite appropriate skin toxicity therapy), discontinue patient from BKM120
 

Grade 4	Omit dose and discontinue patient from BKM120
Fatigue (asthenia)	
Grade 1 or 2	Maintain dose level
Grade 3	
Omit dose until resolved to <math>\leq</math> Grade 1, then:
 
 
If resolved in <math>\leq</math> 7 days, maintain dose level
 
If resolved in <math>></math> 7 days, <math>\downarrow</math> 1 dose level
 

Grade 4	Omit dose and discontinue patient from BKM120
Other non-hematological adverse events	
Grade 1 or 2	Maintain dose level
Grade 3	Omit dose until resolved to $\leq$ Grade 1, then $\downarrow$ 1 dose level
Grade 4	
Omit dose and discontinue patient from study
 
Note: Omit dose for <math>\geq</math> Grade 3 vomiting or Grade 3 nausea only if the vomiting or nausea cannot be controlled with optimal antiemetic

Pneumonitis	See Table 15
** Common Terminology Criteria for Adverse Events (CTCAE) version 4.0.	

Fasting Plasma Glucose (FPG)	

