**Table 15: Management of pneumonitis**

Worst Grade Pneumonitis	Required Investigations	Management of Pneumonitis	BKM120 Dose Adjustment
Grade 1	CT scans with lung windows. Repeat at least every 8 weeks until return to within normal limits.	No specific therapy is required	Administer 100% of BKM120 dose.
Grade 2	CT scan with lung windows. Consider pulmonary function testing includes: spirometry, DL CO , and room air O 2 saturation at rest. Repeat at least every 8 weeks until return to within normal limits. Consider a bronchoscopy with biopsy and / or BAL.	Symptomatic only. Consider corticosteroids if symptoms are troublesome.	Reduce BKM120 dose by 1 dose level (see Table 11) until recovery to ≤ Grade 1. Study treatment may also be interrupted if symptoms are troublesome. Patients will discontinue study treatment if they fail to recover to ≤ Grade 1 within 3 weeks.
Grade 3	CT scan with lung windows and pulmonary function testing includes: spirometry, DL CO , and room air O 2 saturation at rest. Repeat at least every 6 weeks until return to within normal limits. Bronchoscopy with biopsy and / or BAL is recommended.	Consider corticosteroids if infective origin is ruled out. Taper as medically indicated.	Hold treatment with BKM120 until recovery to ≤ Grade 1. May restart study treatment within 3 weeks at a reduced dose (by one level) if evidence of clinical benefit.
Grade 4	CT scan with lung windows and required pulmonary function testing, if possible, includes: spirometry, DL CO , and room air O 2 saturation at rest. Repeat at least every 6 weeks until return to within normal limits. Bronchoscopy with biopsy and / or BAL is recommended if possible.	Consider corticosteroids if infective origin is ruled out. Taper as medically indicated.	Discontinue treatment with BKM120.

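### Holds of 15 to 21 days get opposite continuation instructions for LV dysfunction and pneumonitis, and Table 9 does not settle when rash is a DLT

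*Combined protocol and SAP*

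**What the plan says.** **Continuation.** Section 5.6 sets a general limit: "If a patient requires a dose delay of > 14 days from the intended day of the next scheduled dose", BKM120 is to be stopped. Section 5.7 repeats it ("of the next scheduled dose, then the patient should be discontinued from study treatment"). Section 5.8.1 has the same 14-day figure in mandatory wording, but counts from the previous dose. None of the three names an exception.

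Table 11, for symptomatic LV dysfunction, holds the drug until recovery, resumes one level lower, and adds: "if not resolved to ≤ Grade 1 within 3 weeks, permanently discontinue patient from BKM120". Table 15, for grade 3 pneumonitis, says: "May restart study treatment within 3 weeks at a reduced dose (by one level) if evidence of clinical benefit". For grade 2 pneumonitis Table 15 reduces the dose, allows an interruption if symptoms warrant it, and stops the drug if recovery has not occurred within 3 weeks.

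**DLT definition for rash.** The Dermatologic row of Table 9 counts rash "resulting in interruption of BKM120 for > 21 consecutive days" and gives no grade. The note under the table says: "If a lower grade AE leads to a dose interruption of more than 7 doses of BKM120, this AE will be considered as DLT". The Other adverse events row counts grade 3 or higher events and excludes only alkaline phosphatase. Table 11 keeps grade 1 and 2 rash at the same dose. For grade 3 rash not resolved within 7 days its instruction ends "despite appropriate skin toxicity therapy), discontinue patient from BKM120".

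**Cross-references.** Sections 5.4 and 5.14 carry the same sentence on interrupting or modifying BKM120. Section 5.4 refers the reader to Table 9, section 5.14 to Table 11.

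**The concern.** Two decisions in the trial turn on how long BKM120 has been held: whether the patient may resume, and whether the event is a DLT. The plan uses limits of 7, 14 and 21 days for these and does not say which prevails where they meet.

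On continuation, two patients with the same event and the same hold could be handled differently at the same dose level, one restarted and one stopped. Their exposure would then differ because of the passage consulted rather than because of the drug.

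On the DLT definition, the stake is the primary objective. The MTD comes from counts of 0, 1 or 2 patients in cohorts of three to six, so one ambiguous case can change the decision. The reference in section 5.4 adds to the risk, because it sends the reader to Table 9, and so to the 21-day row, for an interruption rule.

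**Working it through.** **Step 1. Convert doses to days.** Section 5.1 says of BKM120: "It is given every day including weekend days". More than 7 missed doses therefore means a hold of 8 days or more. Let d be the number of consecutive missed daily doses; the restart then falls d + 1 days after the last dose taken.

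**Step 2. Continuation.** In sections 5.6 and 5.7 the delay from the intended day is d, so the drug stops when d > 14, that is d ≥ 15. In section 5.8.1 the gap from the previous dose is d + 1, so it stops when d + 1 > 14, that is d ≥ 14. Tables 11 and 15 do not define when their 3 weeks start; I take 3 weeks as 21 days of hold.

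| Hold d | 5.6 and 5.7 | 5.8.1 | Table 11 (LV), Table 15 (pneumonitis) |
|---|---|---|---|
| up to 13 | may resume | may resume | may resume on recovery |
| 14 | may resume | stop | may resume on recovery |
| 15 to 21 | stop | stop | may resume on recovery |
| 22 or more | stop | stop | stop, or past the restart window |

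The conflict covers 15 to 21 days. A one-day disagreement at d = 14 comes from the different starting points.

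**Step 3. Does the continuation conflict change the DLT count?** No, if the attribution conditions of section 5.5 are met. Symptomatic LV dysfunction is a DLT through the Cardiac row. Grade 3 pneumonitis is one through the Other row. Grade 2 pneumonitis held for 15 days or more is one through the note on more than 7 missed doses. Tables 11 and 15 set no DLT threshold.

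**Step 4. Rash under two readings of Table 9.**

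| Case | Criteria as alternatives | Dermatologic row as a rash-specific exception | Table 11 action |
|---|---|---|---|
| Grade 1 or 2, held 8 to 21 days | DLT, through the note | not a DLT | same dose, so no hold expected |
| Grade 3 | DLT at once, if the Other row covers rash | not a DLT until after 21 days | hold; stop if unresolved after 7 days |

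Under the first reading the 21-day criterion almost never decides anything. Under the second, a grade 3 rash that ended treatment under the 7-day rule is not counted until the stop has lasted more than 21 days, if a permanent stop counts as an interruption at all.

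**Step 5. Consequence for escalation.** The plan's own table (section 13) reproduces. For true DLT rate p,

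P(escalate) = (1 − p)³ + 3p(1 − p)² × (1 − p)³.

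At p = 0.20 this is 0.512 + 0.197 = 0.709, against .71 stated. At 30, 40, 50 and 60% it gives .494, .309, .172 and .082, against .49, .31, .17 and .08. The table is arithmetically right, but it presumes one DLT definition.

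Within a cohort, Table 7 makes the effect of one reclassified patient plain: 0/3 becomes 1/3 (three more enrolled), and 1/6 (escalate) becomes 2/6 (stop, previous level is the MTD).

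The documents do not say how many patients would be reclassified. As sensitivity only: if the stricter count added 2, 5 or 10 percentage points to a 20% rate, the probability of escalating would fall from .71 to .67, .60 or .49. These increments are assumptions.

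**The case against.** The best defence on rash is that section 5.5 and the heading of Table 9 join the criteria as alternatives. The Dermatologic row does not say that rash counts in no other way, so failing that row is not a finding of no DLT. On this reading the note settles lower-grade rash, and Table 11 makes such holds uncommon because grade 1 and 2 rash stay on dose. Most of this stands, and it is the more natural reading. It does not explain why a separate 21-day rash criterion exists, and the note does not reach grade 3 rash. Whether the Other row covers an event that has its own row is left open.

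On continuation, section 5.8.1 is mandatory while Table 11 is headed as recommendations. A restart by day 14 satisfies both texts, and for grade 2 pneumonitis the 3-week clock can run on a reduced dose with no delay. These points narrow the conflict to LV dysfunction, grade 3 pneumonitis and interrupted grade 2 pneumonitis, on days 15 to 21. They do not remove it: if the 14-day limit always prevails, the 3-week limit for held LV dysfunction never operates.

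A reader might infer more than the documents support:

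- That the pneumonitis and LV windows also clash with the 7-dose DLT rule. They set no DLT threshold (Step 3).
- That the 21-day rash criterion is unreachable because treatment stops at 14 days. A DLT does not require staying on drug; section 5.5 counts events less than 28 days after the last dose.
- That rash is frequent enough in Table 6 to fix the size of the problem. The highest figure, 93.8%, comes from a study whose footnote says no patient received 100 mg. The table pools rash with hypersensitivity, allergy and photosensitivity, and incidence says nothing about length of hold.

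**Conclusion.** The plan is wrong as written on two separate points, and both should be corrected.

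(a) For holds of 15 to 21 days, sections 5.6, 5.7 and 5.8.1 require stopping BKM120 where Table 11 (symptomatic LV dysfunction) and Table 15 (grade 3 pneumonitis, grade 2 if interrupted) still allow recovery and restart. The 14-day limit itself has two starting points. This affects exposure and consistent handling, not the DLT count.

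(b) For rash alone, the DLT definition allows two readings. Under one, the 21-day criterion is nearly redundant. Under the other, grade 3 rash that ended treatment is not counted until after 21 days. Grade 3 rash is the weightier case. One patient can decide an escalation, but with no rate for these cases in the documents I put no figure on the bias in the MTD.

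The conclusion assumes daily dosing as planned, 3 weeks meaning 21 days of hold, and that no precedence rule exists outside the text reviewed. It takes no position on which limit is clinically right.

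**What to change.** Reconcile the following passages in one amendment, without this review prescribing any limit:

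- **Discontinuation.** In sections 5.6, 5.7 and 5.8.1, and in the LV row of Table 11 and the pneumonitis rows of Table 15, state which rule takes precedence. Use one starting point for counting the delay, and define when the 3 weeks begin.
- **Rash DLT.** In Table 9, state by grade which criterion governs rash, whether the Other row applies to events with their own row, what lower grade means for a row without a grade, and whether a permanent stop counts as an interruption. Check the result against the grade 3 rash rule in Table 11.
- **Cross-reference.** Make sections 5.4 and 5.14 point to the same table for interruption rules.
- **Past decisions.** Re-check the DLT call for any grade 3 rash, and any rash hold of more than 7 days, already observed, and record which criterion was applied.

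The first three are wording only. The last is a small extra task limited to the affected patients. The sample size and the escalation table need no change.

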#### **5.3 Dose Escalation and Stopping Rules**

The dose-limiting toxicity (DLT), as defined in Section 5.5, will be the basis for determining the maximum tolerated dose (MTD). Any subject who receives at least one dose of the study drug (BKM120) will be included in analysis for DLT. Treatment cohorts will be dosed in escalating order, as outlined in Table 8, only after the safety of the previous dose level has been established, or until an MTD has been determined.

Subsequent dose levels will be opened for treatment as follows:

1) Escalation to the subsequent dose level will occur only after all subjects in the previous cohort have completed the full 7-week course of BKM120-CRT and have been evaluated for safety and toxicity. Safety will be evaluated based on the incidence of adverse events (AEs), physical exam findings, and clinical laboratory test results. A review of the safety data for each cohort will be conducted when all of the above data are available. In the event that an MTD is not reached after dose level 5, the study will be considered to have reached a biologically acceptable dose appropriate for Phase II study. Any further dose escalations or de-escalations will require a protocol amendment.

2) Three patients will initially be enrolled at dose level 1. The following rules apply for the advancement to the next dose level and to determine the MTD (see also Table 7). Enrollment may proceed at the higher dose according to the rules after three patients have been treated for the 2 weeks of BKM120 followed by 7 weeks of BKM120+CRT at a given dose level and safety data have been reviewed. The dose will be increased until a DLT is observed in one subject. Dose limiting toxicity is graded according to the National Cancer Institute’s CTCAE v4.0 (<http://ctep.cancer.gov/forms/CTCAEv4.pdf>).

Once a DLT occurs, additional subjects will be added to the cohort until either a second subject experiences a DLT or six subjects are treated at that dose level. If no additional subject experiences a DLT at the trigger dose-level, further dose escalation as outlined in Table 8 will be explored in cohorts of three subjects.

If two or more subjects experience a DLT at a given dose, then three additional subjects will be treated at the next lower dose, unless six subjects have already been treated at that dose.

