**Table 7: Dose Escalation Criteria**

Number of Subjects per Cohort with DLT During Treatment Period	Dose Escalation Decision
0 out of 3	Enter 3 subjects at the next dose level.
1 out of 3	Enter 3 more subjects at this dose level.  If no additional DLT, proceed to the next dose level.  If an additional DLT occurs (i.e. $\geq$ 2 DLTs/6 subjects), dose

	escalation is stopped and the previous dose level is declared the MTD.
≥ 2	The previous dose level is declared MTD. There is no advancement to higher dose levels.

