#### **5.5 Dose-Limiting Toxicity**

Toxicity will be assessed using the NCI Common Toxicity Criteria for Adverse Events, version 4.0

[http://evs.nci.nih.gov/ftp1/CTCAE/CTCAE\\_4.03\\_2010-06-14\\_QuickReference\\_8.5x11.pdf](http://evs.nci.nih.gov/ftp1/CTCAE/CTCAE_4.03_2010-06-14_QuickReference_8.5x11.pdf) unless

otherwise specified (e.g., hyperglycemia). A dose-limiting toxicity (DLT) is defined as an adverse event or abnormal laboratory value assessed as unrelated to disease, disease progression, inter-current illness, or concomitant medications, and occurs < 28 days following the last dose of BKM120, and meets any of the criteria listed in Table 9.

Whenever a patient experiences toxicity that fulfills the criteria for a DLT (or a potential DLT), treatment with BKM120 will be interrupted (if not otherwise specified) and the toxicity will be followed up as described in section 5.3. Exceptions are CTCAE grade 2 hyperglycemia and CTCAE grade 2 mood alteration, where BKM120 treatment will be continued under appropriate co-medication. The criteria for dose-limiting toxicities are outlined in Table 9.

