	
 
• consider use of oral anti-hyperglycemic therapy such as metformin
 
• check FPG at least weekly for 8 weeks, then continue checking at least every 2 weeks if clinically indicated
 
 
For non-fasting plasma glucose >500 mg/dL (> 27.8 mmol/L) accompanied by signs/symptoms of hyperglycemia (for example, mental status changes, excessive thirst, polyuria), or presence of blood or urine ketones, discontinue BKM120 and following guidance for management of Grade 4 fasting plasma glucose (FPG).

--	--

If the toxicity is due to BKM120, only BKM120 will be dose reduced by one level according to the following schedule below. If toxicity occurs at BKM120 20 mg level, BKM120 will be held.

Dose Level	Dose of BKM120 (mg, daily)
Level E	100
Level D	80
Level C	60
Level B	40
Level A	20

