### 7.1.1.4 Management of Hyperglycemia

In addition to the dose modification and hyperglycemia treatment guidelines in Table 5.

- Under the supervision of an endocrinologist, an insulin regimen should be initiated according to institutional standard of care or the Treat-To-Target Algorithm for Lantus® (Riddle, Rosenstock, and Gerich 2003).
- For any hyperglycemia  $\geq$  grade 1, the patient should continue to follow dietary guidelines provided by the American Diabetes Association (American Diabetes Association 2004).
- For each patient, a maximum of 2 dose reductions will be allowed after which the patient should be discontinued from the study. In addition, a patient must discontinue treatment with BKM120, if after treatment is resumed at a lower dose, hyperglycemia recurs at a worse severity.
- For each patient, once a dose level reduction has occurred, the dose level may not be re-escalated in that patient during future treatment with BKM120.
- Based upon the results of preliminary clinical data and actual laboratory values (e.g., glucose, insulin) generated, the treatment recommendations for study drug induced hyperglycemia may be modified as needed.

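### The second-occurrence DLT rule ends 28 days after the first BKM120 dose and so omits 35 of 49 combination days without a stated reason; few events are affected

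*Combined protocol and SAP*

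**What the plan says.** Section 5.5 counts an event as a DLT if it meets a Table 9 criterion, is not attributed to disease, intercurrent illness or concomitant medication, and "occurs < 28 days following the last dose of BKM120". In section 5.3, Table 7 bases escalation on the "Number of Subjects per Cohort with DLT During Treatment Period", and the next level opens "only after all subjects in the previous cohort have completed the full 7-week course of BKM120-CRT".

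Two rules in the Table 9 footnotes add to its rows. One has no time limit of its own: "If a lower grade AE leads to a dose interruption of more than 7 doses of BKM120, this AE will be considered as DLT". The other concerns a toxicity that was not dose-limiting when it first appeared. If it returns and leads to a dose reduction, it counts only when this happens "within 28 days of the first dose of BKM120, this will be considered a DLT".

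Sections 5.1 and 5.11 give BKM120 alone for 2 weeks and then with cisplatin and radiation for 7 weeks. No section explains why this one rule is tied to the first dose.

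**The concern.** The primary objective is the MTD of BKM120 and cisplatin in combination with radiation. A limit counted from the first dose spends half its length on the lead-in, before any cisplatin or radiation, and ends after CRT week 2. Every other part of the DLT framework runs to the end of treatment or beyond.

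Two patients can therefore have the same recurrence, managed by the same reduction, and be classified differently only because of the week in which it occurred. In a 3+3 design with three to six patients per level, one reclassified event can decide whether a cohort expands or escalation stops. Any difference from a full-course count goes one way, toward fewer DLTs.

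**Working it through.** **1. Plan's own figure.** Section 13 gives escalation probabilities for the 3+3 rule. With DLT rate p, f(p) = (1−p)³ + 3p(1−p)²·(1−p)³. At p = 0.2, 0.3, 0.4, 0.5 and 0.6 this gives 0.709, 0.494, 0.309, 0.172 and 0.082. The stated values are .71, .49, .31, .17 and .08, so the table reproduces.

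**2. Days covered.** Lead-in 14 days + CRT 49 days = 63 BKM120 days.
- Combination days inside the rule: 28 − 14 = 14, and 14/49 = 29%.
- Combination days outside: 49 − 14 = 35, and 35/49 = 71%.
- Cisplatin on CRT days 1 and 8 falls on study days 15 and 22, inside the limit. The remaining 5 of 7 doses start on study day 29.
- If BKM120 stops with a Friday fraction on CRT day 47 (an assumption), 33 of 47 days are outside (70%).

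**3. Which reductions escape every other rule?** Compare section 6 with Table 9.
- Some events are reduced only if they take more than 7 days to resolve: grade 3–4 neutropenia, grade 3 thrombocytopenia, grade 2 bilirubin, grade 2–3 AST/ALT and grade 3 fatigue. Daily dosing is omitted meanwhile, so a Table 9 duration row or the interruption rule applies.
- Febrile neutropenia, grade 4 thrombocytopenia, grade 4 AST/ALT, and grade 3 hyperglycemia, mood and cardiac events meet Table 9 directly.
- Asymptomatic grade 2 hyperglycemia and grade 2 mood alteration are reduced only after 14 days without resolution, which is itself a Table 9 criterion.
- A second QTc event leads to discontinuation, not reduction.

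Clear cases that remain:
- **Grade 2 pneumonitis.** Table 15 says "Reduce BKM120 dose by 1 dose level (see Table 11) until recovery to ≤ Grade 1", with interruption optional. No Table 9 row covers it.
- **Grade 3 rash resolving in 7 days or less.** Table 11 reduces by one level. The Table 9 rash row needs an interruption of more than 21 days.
- **Grade 3 bilirubin resolving in 7 days or less, with ALT or AST at or below 3 × ULN.** Table 11 reduces by one level. The Table 9 rows cover 2–3 × ULN for more than 7 days, or above grade 3.

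The last two hold only if specific rows govern over the generic row for grade 3 or higher events. The footnote implies that they do. It calls a grade 3 AST that resolved within 7 days initially non-dose-limiting, and under the generic row that event would already be a DLT.

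**4. Dose levels.** A second reduction needs two steps down. From 60 mg: 60 → 40 → 20. From 40 mg the first episode leads to 20 mg, and then "If toxicity occurs at BKM120 20 mg level, BKM120 will be held". The cases therefore need a starting dose of 60 mg or more (levels 4–6), assuming no re-escalation. Section 7.1.1.4 states that assumption, under hyperglycemia only: "once a dose level reduction has occurred, the dose level may not be re-escalated in that patient".

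**5. Size.** No recurrence rate is given. Two first-event rates are related.
- Pneumonitis or interstitial lung disease: (5 + 1) cases (section 2.2.8.5) among over 600 patients (section 2.2.8.1), or about 1%.
- Grade 3/4 rash or hypersensitivity at 100 mg (Table 6): 0–11.4% in single-agent studies; 17.0% and 25.0% with trastuzumab.

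As a sensitivity only, suppose the footnote hides 1 percentage point of DLT rate, which is the pneumonitis figure if every case recurred and was missed.
- Counted 30%, full-course 31%: f(0.30) − f(0.31) = 0.4943 − 0.4740 = 0.0203.
- Counted 20%, full-course 21%: f(0.20) − f(0.21) = 0.7086 − 0.6869 = 0.0217.

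Each hidden point thus raises the escalation probability by about 2 points in this range.

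**The case against.** The case for leaving the footnote alone is substantial. A criterion that adds to Table 9 may have its own shorter window, so nothing is strictly contradicted. Most section 6 reductions are already DLTs at any time. Even the footnote's AST example adds nothing late in the course: Table 11 reduces a grade 3 AST only if it takes more than 7 days to resolve, and that already meets Table 9. Recurrent grade 2 pneumonitis needs two separate episodes within nine weeks, not attributed to other causes, and section 2.2.8.5 says causality is unclear. Grade 2 or higher events are reviewed before escalation (section 5.5), the principal investigator decides on escalation (section 5.3), and the monitoring committee sees toxicity data (section 12.2).

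Most of this stands, and it is why the point is small. It does not remove the residual cases in step 3. The reviews would see such an event, but none of them makes it a DLT in the 3+3 count.

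A reader might also infer from section 7.1.1.7 that pneumonitis tends to come after the 28-day limit, since its two dated cases began at about one month and eight weeks. The documents do not support using them here. One case was fatal and the other patient discontinued treatment, so neither could have had a second episode leading to a reduction.

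**Conclusion.** The point holds as an unexplained inconsistency with a narrow reach. The 28-day limit leaves 35 of 49 combination days outside the second-occurrence rule, and classification then depends on the week of the event. The conclusion rests on the pneumonitis case without further conditions on Table 9. For rash and bilirubin it rests on specific rows taking precedence. The restriction to levels 4–6 rests on no re-escalation.

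Two stronger readings are tempting. One is that 71% of DLTs, or of recurrences, would be missed; the figure is a share of days, and all other DLT rules still apply on those days. The other is a large shift in escalation. If second occurrences added 5 to 10 points to a 20–30% DLT rate, spread evenly over 63 days, the escalation probability would rise by about 5 to 12 points. No figure in the documents supports that addition, and the Table 6 rates are first-event rates. The effect on the MTD cannot be computed and is probably small; its direction is under-counting relative to the full-course window used elsewhere.

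**What to change.** In the Table 9 footnote, replace the 28-day limit counted from the first dose with: at any time during BKM120 treatment. Tabulate DLTs for the MTD on that basis.

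The change needs no new data and adds no waiting, because section 5.3 already holds escalation until the full 7-week course is complete and reviewed. Its cost is that slightly more events may count as DLTs, so a cohort may expand to six or escalation may stop sooner. The rule feeds the primary endpoint and the documents do not give enrolment status. Any cohort already decided under the present footnote should therefore be re-tabulated. If the 28-day limit is intended, section 5.5 should state why.
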